## 7.2. Statistical Hypothesis Testing

The primary hypothesis is that NW will improve sleep quality as measured by the Pittsburgh Sleep Quality index (PSQI) relative to sham. On average, compared to the sham, NW will provide a greater reduction in PSQI score measured on day 30 relative to baseline on day 0

Let  $Y_{ij}$  denote the PSQI score for the  $i$ -th participant at their  $j$ -th assessment,  $j=0,1,2$ , where  $j=0$  denotes baseline, and  $i=1,\dots,n$ . Let  $D_i = Y_{i0} - Y_{i1}/2$ , i.e., the difference between the  $i$ -th participant's PSQI score at baseline ( $Y_{i0}$ ) and their average PSQI score across the post-treatment initiation assessment ( $Y_{i1}$ ). The trial will test the hypotheses

$$H_0: \mu_{\text{Active}} \leq \mu_{\text{Sham}} \text{ versus } H_A: \mu_{\text{Active}} > \mu_{\text{Sham}},$$

where  $\mu_{\text{Active}}$  and  $\mu_{\text{Sham}}$  respectively reflect the average difference with NW and sham.

We will evaluate the statistical hypotheses using an equal-variances, two sample t-test. If the equal variance assumption is untenable, we instead will use an unequal-variances, two sample t-test, i.e., Welch's t-test. We will reject the null hypothesis ( $H_0$ ) that change in PSQI from baseline to day 30 resulting from the active NW system is no better than sham when the two-sided p-value is less than or

equal to 0.05 and the direction of the difference favors NW over sham. In this way, the proposed test controls the one-sided type I error rate at 2.5%.

Data will be presented as mean(standard deviation) or median (interquartile range), as appropriate for continuous variables. Categorical variables will be presented as frequency (percentage). Continuous data will be assessed for normality, and transformed as appropriate (e.g. log transformation, square root transformation, etc.). Patient demographics and characteristics will be listed and compared.

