#### **7.4. Interim Monitoring**

The trial will incorporate two interim analyses after 20 and 40 participants in each arm have completed the first 30 days of the trial. Statistical monitoring guidelines will be based on two-sided O'Brien-Fleming boundaries. This conservative interim monitoring plan demands a negligible increase in sample size, so with a MINIMUM of 120 total participants completing, the trial will still be powered at 90% for the targeted benefit. The interim analyses will assess only patient demographics and primary endpoint.

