## **7.7. Implementation**

All statistical analyses will be carried out by the Principal Investigator and/or a PhD Biostatistician.

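### The primary test is run at the full 0.05 after two O'Brien-Fleming looks, so the stated 2.5% one-sided error rate does not hold as written; the excess is small and the fix is wording

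*Protocol*

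**What the plan says.** Protocol section 7.2 names the primary analysis: "We will evaluate the statistical hypotheses using an equal-variances, two sample t-test", with Welch's version if the variances differ. The null hypothesis is rejected when the two-sided p-value is at most "equal to 0.05 and the direction of the difference favors NW over sham". The section then states: "In this way, the proposed test controls the one-sided type I error rate at 2.5" per cent. Its closing sentence sets alpha at 0.05 for all analyses, with no exception for the primary test.

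Section 7.4 adds: "The trial will incorporate two interim analyses after 20 and 40 participants in each arm have completed the first 30 days of the trial". On the rule for these looks it says: "Statistical monitoring guidelines will be based on two-sided O'Brien-Fleming boundaries". On their content: "The interim analyses will assess only patient demographics and primary endpoint". On their cost: "This conservative interim monitoring plan demands a negligible increase in sample size". It gives no boundary values, no spending function and no level for the final test.

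Section 7.3 enrols 240 and treats 60 completers per arm as a minimum. Section 12 lists efficacy, attainment of the primary endpoint and futility as circumstances that may warrant termination.

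The SAP has no section on the primary efficacy test or on the interim looks, so it does not settle the matter.

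On who does the work, section 7.7 says: "All statistical analyses will be carried out by the Principal Investigator and/or a PhD Biostatistician". The SAP ends with the same sentence.

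**The concern.** A 0.05 two-sided test controls one-sided error at 2.5% only if it is the sole chance to claim success. Each look that can stop the trial for efficacy uses part of the 2.5%, so the last test must be made at a lower level. Section 7.2 does not mention the looks, and section 7.4 does not mention the final level.

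Two things are at stake. The first is a stated error rate that is not met on the test that decides the trial. The second is a success rule that depends on which section is followed. Under section 7.2 a final p of 0.047 is a success. If section 7.4 is read as a three-look O'Brien-Fleming plan that includes the last analysis, it is not.

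A related gap concerns access. Comparing the arms against an efficacy boundary needs data split by arm, and no section says who may see them while the trial is running.

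**Working it through.** **Inputs.** Final rule: two-sided p of 0.05 or less, i.e. |Z| ≥ 1.960 (section 7.2). Looks at 20 and 40 per arm with two-sided O'Brien-Fleming boundaries (7.4). At least 60 completers per arm, difference δ = 3, SD σ = 5 (7.3). 120 enrolled per arm (4.1). The boundary values are not in the documents; they are solved below.

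**1. Reproduce the plan's power.** With n per arm, the expected Z is (δ/σ)·√(n/2) = 0.6·√30 = 3.286. Power = Φ(3.286 − 1.960) = 0.908 by normal approximation, and 0.903 by the noncentral t. The normal formula asks for 59 per arm. The stated 90% at 60 per arm is confirmed.

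**2. O'Brien-Fleming boundaries at 20/40/60.** Under the null, the sequential Z statistics are jointly normal with correlation √(n_j/n_k). The boundary is |Z_k| ≥ c/√t_k with t = 1/3, 2/3, 1. Solving for a total two-sided crossing probability of 0.05 gives c = 2.004:

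| Look (per arm) | \|Z\| boundary | Nominal two-sided p |
|---|---|---|
| 20 | 2.004/√(1/3) = 3.471 | 0.0005 |
| 40 | 2.004/√(2/3) = 2.454 | 0.0141 |
| 60 | 2.004 | 0.0451 |

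One-sided error is then 0.0250.

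**3. Same looks, final test as in section 7.2.** Replacing 2.004 by 1.960 gives 0.0273 one-sided and 0.0546 two-sided. The excess is 2.73 − 2.50 = 0.23 percentage points one-sided. With Lan-DeMets O'Brien-Fleming-type spending for the interim boundaries, the figures are 0.0268 and 0.0535.

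**4. More than 60 completers per arm.** The looks stay at 20 and 40, so the information fractions change. The result depends on a choice that the documents leave open.

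| Completers per arm | Boundaries solved for the actual number: one-sided error with final 1.960 | Interim boundaries set for 60 and kept: one-sided error with final 1.960 | Final p needed if boundaries for 60 are kept |
|---|---|---|---|
| 60 | 2.73% | 2.73% | 0.045 |
| 90 | 2.56% | 2.90% | 0.041 |
| 120 | 2.51% | 2.98% | 0.040 |

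A final level fixed at 0.045 is therefore exact only at 60 per arm. With the kept boundaries and 120 per arm, a final Z of 2.004 gives 5.49% two-sided.

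**5. Power after correction.** With the boundaries of step 2 at 60 per arm, power is 0.903 by normal approximation, against 0.908 for a single look. The loss is about 0.4 points.

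**6. Access to interim results.** The passages side by side: section 1.1 calls the trial double-blinded; section 6.4 withholds the device setting from subjects and study staff until unblinding; section 7.1 confines the randomization schedule to unblinded programmers at the sponsor; section 7.7 opens every analysis to the investigator and makes no exception for the looks in 7.4. No section names a monitoring committee or a separate interim statistician.

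**The case against.** **The looks are only guidelines.** Section 7.4 uses that word, and section 12 says only that efficacy may warrant stopping. If a crossing were never acted on, nothing would be inflated. This stands as a condition on the figures. It does not remove the point, because section 12 expressly allows such a stop.

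**O'Brien-Fleming already includes the last look.** A three-look plan ordinarily does. On that reading error is held, but the 0.05 rule in section 7.2 is then the wrong one. Either way the two sections must be reconciled.

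**The excess is trivial.** It is small, and that should be said plainly. A reader might infer serious inflation, of the kind produced by testing at 0.05 at every look. The documents do not support that, because section 7.4 specifies O'Brien-Fleming boundaries. A reader might also take 2.98% as the expected consequence of good retention. That figure holds only if boundaries are set for 60 per arm and never revised, which no section says. Boundaries solved for 120 per arm give 2.51%.

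**The investigator is not said to be unblinded.** Correct. A reader might infer from section 7.7 that the investigator will run unblinded looks. The wording permits but does not require it, names no interim analysis, and does not rule out masked arm codes. Sections 6.4 and 7.1 pull the other way. The primary endpoint is also reported by the participant, which limits direct influence on its scoring. What stands is that no restriction is written down.

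**Conclusion.** The point holds as an unreconciled contradiction with a small numerical effect. If the looks can stop the trial for efficacy and the final test stays at 0.05, the claim of 2.5% one-sided control is wrong: about 2.73% at 60 completers per arm, and between 2.51% and 2.98% at 120 per arm depending on how the interim boundaries are set. These figures rest on classical O'Brien-Fleming boundaries and normal theory for the test statistics. The sample size and the stated 90% power are not in question. The case for correction is that the decisive test carries an inaccurate error statement and an ambiguous success rule, not that the inflation is large.

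The access point is secondary and narrower: the plan does not restrict who sees interim results by arm. It does not show that anyone's blind will be broken.

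**What to change.** 1. In section 7.2, and in a new SAP section on the primary analysis, replace the 0.05 rule for the primary test with an O'Brien-Fleming-type alpha-spending function at two-sided 0.05, evaluated at the actual information fractions. State the planned maximum used to set the interim boundaries. Solve the final critical value from the alpha already spent and the actual number of completers. For orientation, at exactly 20/40/60 per arm the final p is about 0.045 with classical boundaries and 0.046 with Lan-DeMets spending.
2. Exempt the primary test from the sentence in section 7.2 that sets alpha at 0.05 for all analyses, and add cross-references between 7.2 and 7.4.
3. In section 7.4, say whether crossing a boundary stops the trial.
4. In section 7.7 and the SAP, assign the interim analyses by arm to the PhD biostatistician already named, and keep investigators and site staff blinded to them.

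The cost is protocol and SAP wording, settled before a look is taken. No extra participants or staff are needed.

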#### Continuous

variables will be analyzed by category, intervention vs control, by two-sided t-test or Mann-U Whitney, as appropriate. Categorical variables will be compared by Chi-Square test or Fisher's Exact test as appropriate. The change in PSQI score from baseline to day 30 will be tested via repeated measures tests as determined appropriate by a trial statistician.

[figure not shown]
Time-to-event analyses will be conducted to determine time to a reduction of PSQI over the longevity of the study (baseline, visit 2, day 30, day 60, day 90). These analyses may be Kaplan Meier survival curves to determine the time to the median population attaining the 3 point decrease. If appropriate,

univariate cox regression models will be used to determine the hazard ratios of PSQI scores. Additionally multivariable, adjusted, models will be evaluated. All analyses will be conducted at  $\alpha = 0.05$  to alleviate type II errors.

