## 1.2. Schematic

### 1.3. Schedule of Activities

Study Activities Table:

Study Activity	Pre-Tx	Visit 1	Calibration	Start Up Call	Help Calls	Check Up Call 1	Assessment Call	Check Up Call 2	Visit 2	Visit 3	Visit 4
Study Day	Before Day 0	Day 0	Days 0-3	Day 1	Days 2-6 (Optional)	Day 7	Day 14 (+/-3)	Day 21 (+/- 2)	Day 30 (+/- 7)	Day 60 (+/- 7)	Day 90 (+/- 7)
Recruitment	X										
Chart Review	X										
Phone Screen	X										
Inclusion/Exclusion	X	X									
ICF and HIPAA		X									
Modified Dysken I		X a									
AUDIT		X b									
DAST-10		X c									
Demographics		X									
Medical History		X									
Blood Pressure		X							X		
Med Reconciliation		X							X	X	X
PSQI		X					X		X	X	X
PSQI-A		X							X		
ESS		X							X	X	X
ISI		X							X	X	X
PCL-5		X					X		X	X	X
CAPS-5		X									
VR-12 (QOL)		X							X	X	X
TRNS		X							X	X	X

FOSQ-10		X							X		
PHQ-9		X					X		X	X	X
C-SSRS Lifetime		X							X	X	X
Blinding Assessment Questionnaire									X		
NW Likert Scale		X							X	X	X
Daily Use Questionnaire (Days 1-90)				X	X	X	X	X	X	X	X
Calculate Cutoffs/Eligible ?		X									
Dispense NW Devices		X									
Train Subject		X									
Activate Devices		X									
C-SSRS Since Last Contact									X	X	X
Payment of Subject(Bi weekly)	See Reimbursement Section 6.15										
Start Up Call				X							
Calibration			X								
Active/Sham Treatment			Post- Calib. f								
Help Calls Questionnaire (Optional)					X	X		X			
Checkup Phone Call						X		X			
Sham Cross- over to Active Treatment									X		

a—Administered DURING informed consent process to ensure subjects are capable of consent. Subjects must get all responses correct to be enrolled into the study, b-Exclude if score is equal to or greater than 8. c-Exclude if score is greater than 2. f-Only the Active System goes through calibration and on to Active Treatment.

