### 7.3. Sample Size Determination

A total of 240 veterans and active-duty service members will be enrolled (consented) into the study so that even with attrition of up to 50% of study subjects, we can ensure that the study is completed by a MINIMUM of  $n = 120$  participants (60 in each arm) to reach 90% power for rejecting the null hypothesis under the targeted benefit of  $\delta = \mu_{\text{Active}} - \mu_{\text{Sham}} = 3$  points with an equal standard deviation of  $\sigma = 5$  points in each of the two arms. Figure 1 (see below) depicts the power of the trial as a function of the true standardized reduction ( $\delta/\sigma$ ) in the population assuming we enroll and **retain** a MINIMUM of 60 participants in each arm of the proposed trial. If we get more than 60 participants (i.e. less than a 50% attrition rate) this will just make the study results even more powerful.

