**Figure 4: Power Curve (total completers-  $n=120$ , 50% for each arm)**

The rationale for powering the trial to detect a 3-point reduction is two-fold. First, a 3-point reduction constitutes a clinically relevant benefit as this may reflect, for example, a change from 3 (most severe) to 0 (least severe) on a particular item of the PSQI, or a 1-point reduction on three items of the PSQI. Second, assuming a 5-point standard deviation, the targeted 3-point reduction is equivalent to a 0.6 standardized effect, which is plausible as evidenced by a meta-analysis for the observed benefit in previous clinical trials evaluating cognitive behavioral therapies for treating nightmare disorder using the difference between PSQI score at baseline and post-treatment follow-up assessment in which the estimated standard effect size was estimated to be 0.68 (0.34, 1.03). Furthermore, a more recent open-label trial reported a standardized effect size of 1.06. Therefore, the targeted 3-point reduction or 0.6 standardized effect constitutes both a plausible and clinically meaningful benefit in this context.

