#### **7.6. Secondary/Exploratory Analyses**

Secondary and Exploratory analyses will be carried out with appropriate regression modeling techniques and hypothesis tests. In particular, we will use longitudinal data analysis methods, such as generalized estimating equations and generalized linear mixed models, to assess temporal variation in the longitudinal outcome measures, and we will carry out two sample t-tests of the secondary hypotheses.

At the conclusion of the trial, the data will be assessed as both intention to treat (ITT) and per protocol. The effect sizes at the conclusion of the analyses will be compared using standard techniques. If the effect size of the per protocol analysis is greater than 10%, data will be reported as intention to treat to decrease probability of type I errors. Both analyses will follow the outline below:

Secondary outcomes, data will be presented as mean(standard deviation) or median (interquartile range), as appropriate for continuous variables. Categorical variables will be presented as frequency

(percentage). Continuous data will be assessed for normality, and transformed as appropriate (e.g. log transformation, square root transformation, etc.). Patient demographics and characteristics will be listed and compared. Continuous variables will be analyzed by category, intervention vs control, by two-sided t-test or Mann-U Whitney, as appropriate. Categorical variables will be compared by Chi-Square test or Fisher's Exact test as appropriate. Longitudinal data will be analyzed by repeated measures tests as appropriate for the variables.

Repeated measure ANOVA will be used to determine the difference in responses at the time points between groups for all survey types and questions, as appropriate. If determined inappropriate Poisson regression models will be used to determine the univariate, univariable, effect size.

Upon secondary outcomes analysis, multivariable, adjusted, models will be used to determine controlled effect sizes. Each variable with a p-value of 0.25 or less in standard distribution test will be included in the model. Backward stepwise regression modeling may be used to best fit the model.

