Time-to-event analyses will be conducted to determine time to survey effects over the longevity of the study (baseline, visit 2, day 30, day 60, day 90) for all survey results within the secondary outcomes. Univariate Cox regression models may be used to determine hazard ratios for the survey scores if appropriate.

Correlation coefficients (i.e. Spearman, Pearson) may be used to determine the inter-survey reliability. If determined to be reliable, multivariate analyses may be conducted for surveys.

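### Time-to-event analyses run to Day 90, across the sham crossover scheduled at Day 30, so a between-arm hazard ratio would be diluted (wrong as written; should-fix)

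*Protocol*

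**What the plan says.** - **Length of the randomised phase.** The synopsis (protocol 1.1) gives 30 randomised days and then a 60-day open-label extension. The schedule of activities (1.3) carries the row "Sham Cross- over to Active Treatment", marked at Visit 2, which is Day 30.
- **Time-to-event, PSQI.** Section 7.2 plans analyses to "determine time to a reduction of PSQI over the longevity of the study (baseline, visit 2, day 30, day 60, day 90". It names Kaplan-Meier curves for a 3-point fall and, if appropriate, Cox models. It does not name the Cox covariate.
- **Time-to-event, secondary surveys.** Section 7.6, repeated in the SAP: "Time-to-event analyses will be conducted to determine time to survey effects over the longevity of the study", with the same visit list.
- **Repeated measures.** Section 7.6 and the SAP: "Repeated measure ANOVA will be used to determine the difference in responses at the time points between groups for all survey types and questions". No last day is given. The PSQI repeated-measures test in section 7.2 is different: it is confined to the change from baseline to Day 30.
- **Handling of the crossover.** Neither document censors at crossover, stops these analyses at Day 30, or treats Days 60 and 90 separately.
- **Conflicting text.** Sections 2.3, 6.5 and 6.6 say that the Sham System or sham group never delivers or receives the intervention. That does not agree with the crossover row.

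**The concern.** On the schedule's account, everyone has the active device after Visit 2. Days 60 and 90 then compare longer with shorter active treatment, not Active with Sham. A hazard ratio fitted through Day 90 blends the two comparisons, and the ratio between arms changes at Day 30 by design, so the proportional-hazards assumption fails. A group main effect from a repeated-measures ANOVA that includes Days 60 and 90 is averaged down in the same way.

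The visit list has two errors of its own. Visit 2 and Day 30 are listed as separate time points although they are one visit. Day 14, the only other PSQI assessment before the crossover, is left out.

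At stake is the reading of the supportive PSQI analysis and of most secondary surveys. A real benefit could appear small or absent because of the analysis window.

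**Working it through.** **1. The plan's own figure.** Inputs from section 7.3: "participants (60 in each arm) to reach 90% power for rejecting the null hypothesis", "assuming a 5-point standard deviation" and "the targeted 3-point reduction is equivalent to a 0.6 standardized effect". Section 7.2 sets a two-sided 0.05 test.

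- Standard error = 5 × √(2/60) = 0.913; 3 / 0.913 = 3.286.
- Normal power = Φ(3.286 − 1.96) = 0.908; with the t distribution, 0.903.
- With an O'Brien-Fleming final critical value of 2.004: Φ(3.286 − 2.004) = 0.900.

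The stated 90% reproduces. It concerns Day 30 only and is not touched by the crossover. The documents give no design figure for the time-to-event or repeated-measures analyses.

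**2. Time to a 3-point fall.** Assumptions not in the documents:
- correlation 0.5 between visits;
- mean sham improvement of 1 or 2 points, with Active 3 points better;
- sham gaining all, or half, of the 3 points after Day 30.

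The implied Day 30 proportions with a fall of at least 3 points are Φ((mean − 3)/5). For sham these are Φ(−0.4) = 34% or Φ(−0.2) = 42%. For Active they are Φ(0.2) = 58% or Φ(0.4) = 66%.

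The event is the first visit with a fall of at least 3 points. Cox model with Efron ties, 60 per arm, simulated:

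| Visits used | Sham after Day 30 | Hazard ratio | Power |
|---|---|---|---|
| Days 14, 30 | not used | about 1.9 | 80–82% |
| Days 30, 60, 90 | half catch-up | about 1.6 | 61–67% |
| Days 30, 60, 90 | full catch-up | about 1.4 | 32–39% |

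The ranges cover both sham means and separate sets of simulations. At half catch-up, for example, one set gave 64–67% and a 3,000-run repeat gave 61–62%. A log-rank test shows the same pattern over Days 30, 60 and 90: power 83–87% if nothing changes at Day 30, 60–63% at half catch-up and 32–36% at full catch-up.

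**3. Group main effect in a repeated-measures ANOVA.** For k visits with correlation ρ, the SD of a person's mean is 5 × √((1 + (k − 1)ρ)/k). At 60 per arm:

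| Visits averaged | Mean difference | Power at ρ = 0.5 (range, ρ = 0.7 to 0.3) |
|---|---|---|
| Days 14, 30 | (3 + 3)/2 = 3.0 | 96% (94–98%) |
| Days 30, 60, 90, half catch-up | (3 + 1.5 + 1.5)/3 = 2.0 | 76% (68–85%) |
| Days 30, 60, 90, full catch-up | (3 + 0 + 0)/3 = 1.0 | 27% (23–32%) |
| Days 14, 30, 60, 90, full catch-up | (3 + 3 + 0 + 0)/4 = 1.5 | 54% (46–66%) |

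The group-by-time test behaves differently. With differences 3, 0, 0 (mean 1), the noncentrality is 30 × (4 + 1 + 1) / (25 × 0.5) = 14.4 on 2 and 236 degrees of freedom, giving 93% power (82–99% for ρ = 0.3 to 0.7). The dilution therefore belongs to the averaged effect, not to every term of the ANOVA.

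**4. Which surveys are exposed.** Under the schedule, PSQI-A and FOSQ-10 are not collected after Day 30, so a later window cannot affect them. PSQI, PCL-5, PHQ-9, ESS, ISI, VR-12, TRNS and the NW Likert scale are collected at Days 60 and 90. Of the efficacy scales, only PSQI, PCL-5 and PHQ-9 are also collected at Day 14.

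**The case against.** Several points on the other side are sound.

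- **The arm comparison is not written.** The time-to-event text does not say that Cox or Kaplan-Meier compares arms. Pooled curves, or curves by sequence, would be descriptive and harmless. An arm comparison is the likely purpose, since the synopsis lists greater improvement under Active than Sham among the outcomes, but it remains an inference.
- **The repeated-measures window is partly closed already.** A reader might infer that all repeated-measures comparisons run to Day 90. The PSQI test in section 7.2 stops at Day 30. For the section 7.6 ANOVA, Day 90 is the natural reading but is not stated.
- **The effect is not erased.** A reader might infer that it is. Only a contrast at Day 60 or Day 90 alone, under full catch-up, has an expected difference of zero. Analyses that include Day 30 keep part of the effect, and the 27% power applies to an average that the plan does not name.
- **Direction and standing.** The bias is toward no effect, so it would not create a false efficacy claim. The secondary objectives are framed from Day 0 to Day 30, and the Kaplan-Meier and Cox wording is hedged.
- **The crossover itself is contradicted.** If sham were never switched, this dilution would not arise. Days 31 to 90 would still be labelled open label, so they would not extend the blinded comparison.

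These points limit scope and severity. They do not supply the missing censoring rule or end day.

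**Conclusion.** The time-to-event plan is wrong as written: its window crosses the scheduled sham switch and no rule deals with it. The repeated-measures ANOVA needs a stated last day for the same reason. The direction, toward no difference, is clear if arms are compared and sham switches at Day 30. The size is not fixed by the documents, because it depends on how far sham catches up, how much sham improves before Day 30, and the correlation between visits. The figures above are illustrations under those assumptions.

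A reader might go further and infer that the trial's main result is compromised. The documents do not support that: the primary comparison is a Day 30 t-test, and its 90% power reproduces. The point is therefore should-fix.

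**What to change.** 1. In protocol sections 7.2 and 7.6 and in the SAP, limit every between-arm time-to-event and repeated-measures comparison to visits up to Day 30. Use Days 14 and 30 for PSQI, PCL-5 and PHQ-9, and Day 30 alone for the other surveys. Censor at the Day 30 visit.
2. State the Cox covariate, and give the ANOVA an explicit last visit.
3. Correct the visit list: one entry for Visit 2 (Day 30), and add Day 14 where the survey is collected.
4. Report Days 60 and 90 descriptively by original assignment.
5. Reconcile the crossover row in section 1.3 with the statements in sections 2.3, 6.5 and 6.6.

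Optionally, the proportion with a PSQI fall of at least 3 points at Day 30 could replace the Cox analysis. That is a preference, since stopping at Day 30 already removes the contamination.

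The cost is wording only: no new data, visits or participants, and no change to the primary test or the sample size.

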## **6.10. Day 14: Patient Questionnaire Assessment**

Participants will complete questionnaires on Day 14 (+7 days). Study coordinator will contact participants on Day 16 if the questionnaires have not yet been completed. Questionnaires to be completed:

- a. Administer the PCL-5.
- b. Administer the PHQ-9
- c. Pittsburgh Sleep Quality Index (PSQI)

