## **6.12. Day 30: Visit 2 - In person follow up**

The following events/assessments will occur at the in-person 30-day (+ 7 days) visit.

Health assessments

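### Time-to-event analyses run to Day 90 across the Day 30 sham crossover with no censoring or confirmation rule, and for six of eight secondary surveys they reduce to a Day 30 yes/no

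*Protocol*

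**What the plan says.** Section 7.2 states that time-to-event analyses of PSQI reduction will be done "over the longevity of the study (baseline, visit 2, day 30, day 60, day 90"). It then adds: "These analyses may be Kaplan Meier survival curves to determine the time to the median population attaining the 3 point decrease". Cox models follow if judged appropriate. Section 7.6 and the SAP commit to the same type of analysis "for all survey results within the secondary outcomes", without naming an event threshold for any of them.

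Other parts of the protocol bear on this:

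- Section 6.12 is headed "Day 30: Visit 2 - In person follow up", so two entries in the visit list are the same visit.
- Section 6.10 says "Participants will complete questionnaires on Day 14 (+7 days"), and the PSQI is one of those questionnaires. The list in 7.2 leaves it out.
- The synopsis gives 30 randomised days followed by a 60-day open-label extension. The Schedule of Activities places the sham crossover at Visit 2.
- Section 7.3 sets the 3-point target and the SD: "Second, assuming a 5-point standard deviation, the targeted 3-point reduction is equivalent to a 0.6 standardized effect".

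**The concern.** A time-to-event comparison needs a defined event, a follow-up period in which the arms differ as randomised, and enough observation times for timing to mean something. The plan is weak on all three.

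The event is attaining a 3-point fall, with no statement on whether it must be confirmed or sustained. Three points is only 0.6 of the assumed SD, so many participants would cross the line with no change in the arm mean, and each further visit gives another chance.

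The curve runs to Day 90, but from Day 30 the sham arm is on active treatment. With no censoring at crossover, events at Days 60 and 90 compare active with crossed-over sham. If the device works, responses it produces in former sham participants are counted for sham.

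Most secondary surveys have one follow-up in the randomised period, so a hazard ratio confined to that period carries no timing information.

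At stake is a published median time to response, or a set of hazard ratios, that readers would take as evidence of speed of effect.

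**Working it through.** **1. The plan's own figure.** Section 7.3 gives 60 completers per arm, difference 3, SD 5 and 90% power; section 7.2 gives two-sided 0.05. The standard error is 5 x sqrt(2/60) = 0.913, and 3/0.913 = 3.286. Power = Phi(3.286 - 1.960) = 90.8% (90.3% with the noncentral t). The plan's figure reproduces. It also shows that the SD of 5 is used for change scores, because section 7.2 defines the means as average changes.

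**2. One visit, no mean change.** P(fall of 3 or more) = 1 - Phi(3/5) = 27.4%. The strata boundaries (15 and below, 16 and above) imply whole-number scores. With a continuity cut at 2.5, the figure is 1 - Phi(2.5/5) = 30.9%.

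**3. Several visits.** Assume changes are normal with mean 0, SD 5 and a common correlation rho between visits. Then P(at least one fall in k visits) = 1 - integral of phi(x) x [Phi((c/5 - sqrt(rho) x)/sqrt(1 - rho))]^k dx. The documents give no rho. A shared baseline with equal independent errors implies 0.5. Entries are percentages for cut 3 / cut 2.5.

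| Visits counted | rho 0.3 | rho 0.5 | rho 0.7 | rho 0.9 |
|---|---|---|---|---|
| Days 14, 30 | 43.8 / 48.3 | 41.1 / 45.4 | 37.9 / 41.9 | 33.4 / 37.2 |
| Days 30, 60, 90 | 54.6 / 59.4 | 49.6 / 54.1 | 44.1 / 48.3 | 36.7 / 40.6 |
| Days 14, 30, 60, 90 | 62.2 / 66.9 | 55.6 / 60.1 | 48.3 / 52.6 | 38.9 / 42.9 |

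**4. When the median is passed.** Over Days 30, 60 and 90, 50% is exceeded only if rho is below 0.49 (cut 3) or 0.65 (cut 2.5). Over all four PSQIs the limits are 0.66 and 0.76. With Days 14 and 30 alone, it is never exceeded at cut 3, and only for rho below 0.17 at cut 2.5.

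**5. A small mean shift.** At rho 0.5, a mean improvement of 1.03 points (cut 3) or 0.53 points (cut 2.5) brings Days 14 and 30 to 50%. Entry requires a PSQI of at least 10, on the score that also serves as baseline, so regression to the mean pushes both arms in this direction. The documents do not allow its size to be estimated.

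**6. Effect of a confirmation rule.** Requiring two consecutive falls among the four visits lowers the no-change figure to 24-29% (rho 0.5-0.7, both cuts).

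**7. If 5 is the SD of a single score.** With within-person correlation r, the SD of change is 5 x sqrt(2(1 - r)): 5.00 at r = 0.5 and 3.87 at r = 0.7. The Days 30/60/90 figure is then 41.8-54.1%, so the picture is similar.

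**8. Secondary surveys in the Schedule of Activities.**

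| Survey | Follow-ups up to Day 30 | After Day 30 |
|---|---|---|
| PCL-5, PHQ-9 | Days 14, 30 | Days 60, 90 |
| ISI, VR-12, TRNS, NW Likert | Day 30 | Days 60, 90 |
| PSQI-A, FOSQ-10 | Day 30 | none |

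Six of eight have one follow-up before crossover, and two of those have one in the whole study. The SAP also says the TRNS yields no score, so no total-score event can be defined for it.

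**The case against.** The strongest reply is that little hangs on this. Kaplan-Meier is only a possible form, Cox models are conditional, and the efficacy claim rests on the Day 30 two-sample t-test. That is right about the primary conclusion. It does not remove the point, because sections 7.2 and 7.6 and the SAP all say that time-to-event analyses will be done.

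A second reply is that crossings seen only at visits are ordinary interval censoring and suit a discrete-time method. That is fair for timing within the PSQI schedule. It does not deal with the crossover, or with surveys that have one follow-up.

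Some stronger readings are tempting but not supported:

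- A reader might infer that an arm with no true change would reach the median. That depends on an undocumented correlation and on visits after Day 30. Within the randomised period the figure is 38-45%, and no untreated sham arm exists through Day 90.
- A reader might infer that the plan defines the event as one unconfirmed drop. It does not: first crossing is the natural reading, but the event is undefined.
- A reader might treat the whole SD of 5 as measurement noise. It also contains real differences between people in how much they change.
- A reader might say the 3 points is purely a between-arm difference. Section 7.3 also gives an item-level rationale for it, though not a responder definition.
- The ESS might be counted among the affected surveys. It is a primary safety measure, and the text covers only secondary outcomes.
- A reader might argue that chance events dilute the contrast. That is no ground for the change below, which keeps the same 3-point cut.

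**Conclusion.** The point holds as a recommended change to secondary and supportive analyses. The firmest parts need no assumption: follow-up to Day 90 crosses the Day 30 sham crossover without a censoring rule, the visit list repeats one visit and omits another, no confirmation is required, and six of eight secondary surveys reduce to a yes/no at Day 30 within randomised follow-up.

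The size of the event problem is about 27-31% of participants at one visit with no mean change. It rests on normal changes with SD 5. The multi-visit ranges of 38-45% by Day 30 and 44-54% over Days 30, 60 and 90 also rest on an assumed correlation of 0.5-0.7. On those figures, a median time to response could be reached or nearly reached with little or no mean effect. The primary t-test and its power are not in question.

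**What to change.** In section 7.2, replace the between-arm PSQI time-to-event analysis with the proportion in each arm whose PSQI has fallen by at least 3 points at Day 30. Report the Active minus Sham risk difference with a 95% interval, stratified by the randomisation strata (site and baseline PSQI group), and label it supportive to the primary t-test.

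In section 7.6 and the SAP, drop time-to-event analysis of the secondary surveys and report the Day 30 between-arm difference, item by item for the TRNS. Keep the planned generalised estimating equations and mixed models. Present Day 60 and Day 90 results as descriptive open-label data.

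The cost is wording and the loss of a time-to-response curve. The responder comparison also has less power than the mean comparison. Under the plan's difference of 3 and SD of 5, the rates are 1 - Phi(0.6) = 27.4% and 1 - Phi(0) = 50%. With 60 per arm, the pooled rate is 38.7%, the null standard error is sqrt(2 x 0.387 x 0.613/60) = 0.0889, and the alternative standard error is sqrt((0.274 x 0.726 + 0.25)/60) = 0.0865. Power is Phi((0.226 - 1.96 x 0.0889)/0.0865), about 72%, against 90% for the t-test. It should therefore stay supportive.
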